4.3. Exclusion Criteria

The presence of any of the following will exclude a subject from enrollment:

1. Subject with the any of the following prior treatments for underlying disease:
 - Disease modifying agents (eg, immune-modulatory drug [IMiDs such as lenalidomide])
 - Except if the subject received \leq 1 week of treatment with a disease modifying agent \geq 8 weeks from W1D1, at the investigator's discretion.
 - Hypomethylating agents
 - Subjects may be enrolled at the investigator's discretion contingent that the subject received no more than 2 injections of HMA. The last dose must be \geq 8 weeks from the date of W1D1.
 - Luspatercept (ACE-536) or sotatercept (ACE-011)
 - Allogeneic and/or autologous hematopoietic cell transplant
2. Subject with myelodysplastic/myeloproliferative neoplasms (MDS/MPN) according to WHO 2016 classification (ie, chronic myelomonocytic leukemia (CMML), atypical chronic myeloid leukemia (aCML), BCR-ABL12, juvenile myelomonocytic leukemia (JMML), MDS/MPN unclassifiable.

¹ True abstinence is acceptable when this is in line with the preferred and usual lifestyle of the subject. (Periodic abstinence [eg, calendar, ovulation, symptothermal, post-ovulation methods] and withdrawal are not acceptable methods of contraception).

² Highly effective contraception is defined in this protocol as the following (information will also appear in the ICF): Hormonal contraception (ie, birth control pills); intrauterine device (IUD); tubal ligation (tying your tubes); or a partner with a successful vasectomy.

3. Subject with secondary MDS, ie, MDS that is known to have arisen as the result of chemical injury or treatment with chemotherapy and/or radiation for other diseases.
4. Subject with known clinically significant anemia due to iron, vitamin B12, or folate deficiencies, or autoimmune or hereditary hemolytic anemia, or hypothyroidism, or any type of known clinically significant bleeding or sequestration. Subject with drug induced anemia (eg, mycophenolate).
 - Iron deficiency to be determined by serum ferritin < 100 µg/L and additional testing if clinically indicated (eg, calculated transferrin saturation [iron/total iron binding capacity ≤ 20%] or bone marrow aspirate stain for iron).
5. Subject with known history of diagnosis of AML
6. Subject receiving any of the following treatment within 8 weeks prior to W1D1:
 - Anticancer cytotoxic chemotherapeutic agent or treatment
 - ESAs
 - Granulocyte colony-stimulating factor (G-CSF), granulocyte-macrophage colony-stimulating factor (GM-CSF), unless given for treatment of febrile neutropenia
 - Immunosuppressive therapy for MDS
 - Systemic corticosteroid, except for subjects on a stable or decreasing dose for ≥ 1 week prior to W1D1 for medical conditions other than MDS
 - Other RBC hematopoietic growth factors (eg, Interleukin-3)
 - Androgens, unless to treat hypogonadism
 - Hydroxyurea, anagrelide
 - Oral retinoids
 - Arsenic trioxide
 - Interferon and interleukins
 - Investigational drug or device, or approved therapy for investigational use (if 5 times the half-life of the previous investigational drug exceeds 8 weeks, then the time of exclusion should be extended up to 5 times the half-life of the investigational drug)
7. Subject with uncontrolled hypertension, defined as repeated elevations of systolic blood pressure (SBP) of ≥ 150 mmHg and/or diastolic blood pressure (DBP) ≥ 100 mmHg despite adequate treatment, or with a history of hypertensive crisis or hypertensive encephalopathy.
8. Subject with any of the following laboratory abnormalities:
 - Absolute neutrophil count (ANC) < 500/µL (0.5 x 10⁹/L)
 - Platelet count < 30,000/µL (30 x 10⁹/L) (Exclude subjects that may be at risk of bleeding regardless of platelet counts. This includes [but is not limited to] subjects currently using aspirin or heparin, immediately after surgery, or easily causes

bleeding such as nasal bleeding or subcutaneous bleeding or previous episode of major bleeding where the cause was not effectively treated.)

- Estimated glomerular filtration rate (eGFR) < 40 mL/min/1.73 m² (via the 4-variable modification of diet in renal disease [MDRD] formula, [Appendix G](#))
- Serum aspartate aminotransferase/serum glutamic oxaloacetic transaminase (AST/SGOT) or alanine aminotransferase/serum glutamic pyruvic transaminase (ALT/SGPT) ≥ 3.0 x upper limit of normal (ULN)
- Total bilirubin ≥ 2.0 x ULN.
 - Higher levels are acceptable if these can be attributed to active red blood cell precursor destruction within the bone marrow (ie, ineffective erythropoiesis) or in the presence of known history of Gilbert Syndrome.

9. Subject with prior history of malignancies, other than MDS, unless the subject has been free of the disease for ≥ 5 years. However, subjects with the following history/concurrent conditions are allowed if considered as curatively treated:

- Basal or squamous cell carcinoma of the skin
- Carcinoma in situ of the cervix
- Carcinoma in situ of the breast
- Incidental histologic finding of prostate cancer (T1a or T1b using the tumor, nodes, metastasis [TNM] clinical staging system)

10. Subject with major surgery within 8 weeks prior to W1D1. Subjects must have completely recovered from any previous surgery prior to W1D1

11. Subject with history of cerebrovascular accident (including ischemic, embolic, and hemorrhagic cerebrovascular accident), transient ischemic attack, deep venous thrombosis (DVT; including proximal and distal), pulmonary or arterial embolism, arterial thrombosis or other venous thrombosis within 6 months prior to W1D1
Note: prior superficial thrombophlebitis is not an exclusion criterion.

12. Subject with the following cardiac conditions within 6 months prior to W1D1: myocardial infarction, uncontrolled angina, acute decompensated cardiac failure or New York Heart Association (NYHA) Class III-IV heart failure, or uncontrolled cardiac arrhythmia as determined by the investigator. Subjects with a known ejection fraction < 35%, confirmed by a local echocardiogram (ECHO) or multi-gated acquisition (MUGA) scan performed within 6 months prior to W1D1.

13. Subject with uncontrolled systemic fungal, bacterial, or viral infection (defined as ongoing signs/symptoms related to the infection without improvement despite appropriate antibiotics, antiviral therapy, and/or other treatment).

14. Subject with known human immunodeficiency virus (HIV), known evidence of active infectious hepatitis B, and/or known evidence of active hepatitis C. Local laboratory testing confirming HIV, hepatitis B, and hepatitis C status should not have been performed beyond 4 weeks prior to the date of ICF signature.

15. Subject with history of severe allergic or anaphylactic reactions or hypersensitivity to recombinant proteins or excipients in luspatercept (see current IB).
16. Pregnant or breastfeeding females.
17. Subject has any significant medical condition, laboratory abnormality, psychiatric illness, or is considered vulnerable by local regulations (eg, imprisoned or institutionalized) that would prevent the subject from participating in the study.
18. Subject has any condition including the presence of laboratory abnormalities, which places the subject at unacceptable risk if he/she were to participate in the study.
19. Subject has any condition or receives concomitant medication that confounds the ability to interpret data from the study.
20. Subject has history of active SARS-CoV-2 infection within 4 weeks prior to screening, unless the subject has adequately recovered from COVID-19 symptoms and related complications as per investigator's discretion and following a discussion with the Medical Monitor. Use of a live COVID-19 vaccine is prohibited within 4 weeks prior to W1D1.

5. TABLE OF EVENTS

Table 3: Table of Events

	Screening	Treatment Period								Post-treatment Follow-up			
							Efficacy Assessment Independent of any dose delays						
Section	Day -35 to -1	W1D1 Visit	W2D1 Visit	W3D1 Visit	3-wkly Visits W4D1 W7D1 W10D1 etc.	Other Visits	24-Wk MDS Assessment Visit D169	Every 24 wks D337 D505 etc.	EOT Visit ^a	42-Day Follow-up	Long Term Follow-up	End of Study	
Section										6.2.2/11.1	6.3.1	6.3.2	11.2
Time window				±2 days	±2 days	±2 days	±2 days	±14days ^b	±14days ^b		+2 days	±7 days	

Note:

Weekly visits as displayed above represent visits as they are scheduled if dosing occurs without any dose delays. In the event of dose delays (eg, due to adverse events) the next dosing visit (every 3 weeks for luspatercept) and associated assessments should be delayed accordingly. Assessments to monitor the condition of the subject should be recorded as unscheduled visits. Please note that efficacy assessments (MDS Disease assessments) always occur at the designated days after W1D1 as indicated above. Dose delays do not affect the timing of these assessments.

Informed Consent	6.1	X	–	–	–	–	–	–	–	–	–	–	–
Inclusion/Exclusion Evaluation	6.1	X	–	–	–	–	–	–	–	–	–	–	–
Physical Examination	6.1.5	X	–	–	–	–	–	X	X	X	–	–	–
Demographics	6.1.3	X	–	–	–	–	–	–	–	–	–	–	–
Medical History	6.1.4	X	–	–	–	–	–	–	–	–	–	–	–
HIV and Hep B/C Status	6.1.4.1	X	–	–	–	–	–	–	–	–	–	–	–
Prior RBC and Platelet Transfusions	6.1.2	X	–	–	–	–	–	–	–	–	–	–	–

Table 3: Table of Events (Continued)

		Screening	Treatment Period							Post-treatment Follow-up			
								Efficacy Assessment Independent of any dose delays					
Section	Day -35 to -1	W1D1 Visit	W2D1 Visit	W3D1 Visit	3-wkly Visits W4D1 W7D1 W10D1 etc.	Other Visits	24-Wk MDS Assessment Visit D169	Every 24 wks D337 D505 etc.	EOT Visit ^a	42-Day Follow-up	Long Term Follow-up	End of Study	
Section										6.2.2/11.1	6.3.1	6.3.2	11.2
Time window				±2 days	±2 days	±2 days	±2 days	±14days ^b	±14days ^b		+2 days	±7 days	
INVESTIGATIONAL PRODUCT (IP)													
IP Administration and Accountability Luspatercept	7	—	X	—	—	X	—	—	—	—	—	—	
SAFETY ASSESSMENTS													
ECOG Performance Status	6.1.7	X	X	—	—	X	—	X	X	X	—	—	
Urinalysis	6.1.13	X	X	—	—	Every 12 weeks ie, W13D1, W25D1, etc.	—	—	—	—	—	—	
ECG (12-lead)	6.1.8	X	—	—	—	—	—	—	—	—	—	—	
Pregnancy Test and Counseling	6.1.14	X	X	—	—	X	—	—	—	X	—	—	
Adverse events	6.1.19/10	Continuous, after signing informed consent until 42 days after last IP administration								—	—	—	

Table 3: Table of Events (Continued)

		Screening	Treatment Period							Post-treatment Follow-up		
								Efficacy Assessment Independent of any dose delays				
Section	Day -35 to -1	W1D1 Visit	W2D1 Visit	W3D1 Visit	3-wkly Visits W4D1 W7D1 W10D1 etc.	Other Visits	24-Wk MDS Assessment Visit D169	Every 24 wks D337 D505 etc.	EOT Visit ^a	42-Day Follow-up	Long Term Follow-up	End of Study
Section										6.2.2/11.1	6.3.1	6.3.2
Time window				±2 days	±2 days	±2 days	±2 days	±14days ^b	±14days ^b		+2 days	±7 days
SAFETY ASSESSMENTS (Continued)												
Prior and Concomitant medications/ procedures	6.1.18/8	Continuous, 8 weeks prior to W1D1 until 42 days after last IP administration or until the EOT Visit, whichever occurs later									—	—
Vital Signs (Height to be measured only at screening)	6.1.6	X	X	X	X	X	—	X	X	X	—	—
Serum Chemistry ^c	6.1.10	X	X	—	—	X	—	X	X	X	—	—

Table 3: Table of Events (Continued)

		Screening	Treatment Period								Post-treatment Follow-up		
									Efficacy Assessment Independent of any dose delays				
Section	Day - 35 to -1	W1D1 Visit	W2D1 Visit	W3D1 Visit	3-wkly Visits W4D1 W7D1 W10D1 etc.	Other Visits	24-Wk MDS Assessment Visit D169	Every 24 wks D337 D505 etc.	EOT Visit ^a	42-Day Follow-up	Long Term Follow-up	End of Study	
Section										6.2.2/11.1	6.3.1	6.3.2	11.2
Time window			±2 days	±2 days	±2 days	±2 days	±14days ^b	±14days ^b		+2 days	±7 days		
EFFICACY ASSESSMENTS													
Hematology ^c	6.1.9	X	X	X	X	X	X	–	X	X	X	–	–
Serum EPO	6.1.11	X	–	–	–	–	Every 6 weeks: ie, W7D1 W13D1 etc.	–	X	X	X	–	–
Serum Ferritin and other iron-related markers	6.1.12	X	X	–	–	X	–	X	X	X	–	–	–
Transfusion Data Collection and Assessment	6.4.1	Assess and record on ongoing basis (prior to each dose of IP) until 8 weeks after last dose of IP or the End of Treatment Visit, whichever occurs later. Clinical site staff must confirm (and document in the subject's source record) if any transfusions were received by the subject (including any at outside local institutions in between study visits) prior to each IP administration. In addition to local procedures in place at the site to capture this information, a patient transfusion diary will be provided to subjects and will be reviewed by the site when/if returned by the subject.										–	–
MDS Disease Assessment	6.4.2	–	–	–	–	–	–	–	X	X	X	–	–
BMA and PB for Cytomorphology and Cytogenetic testing ^{d,e}	6.1.1	X	–	–	–	–	–	–	X	X	X	–	–

Table 3: Table of Events (Continued)

	Screening	Treatment Period									Post-treatment Follow-up		
								Efficacy Assessment Independent of any dose delays					
Section	Day -35 to -1	W1D1 Visit	W2D1 Visit	W3D1 Visit	3-wkly Visits W4D1 W7D1 W10D1 etc.	Other Visits	24-Wk MDS Assessment Visit D169	Every 24 wks D337 D505 etc.	EOT Visit ^a	42-Day Follow-up	Long Term Follow-up	End of Study	
Section										6.2.2/11.1	6.3.1	6.3.2	11.2
Time window				±2 days	±2 days	±2 days	±2 days	±14days ^b	±14days ^b		+2 days	±7 days	
EXPLORATORY/BIOMARKER ASSESSMENTS													
PB for Exploratory Biomarkers (eg, soluble biomarkers, MDS-associated molecular mutations and other markers of drug MOA)	6.1.1 6.7	X	–	–	X	W10D1 W34D1 only	–	X	X	X	–	–	–
BMA for Exploratory Biomarkers (eg, soluble biomarkers, MDS-associated molecular mutations, erythroid differentiation and other markers of drug MOA) ^f	6.1.1 6.7	X	–	–	–	–	–	X	X	X	–	–	–
SARS-COV-2 Serology testing	6.7	X	–	–	–	–	–	–	–	X	–	–	–

Table 3: Table of Events (Continued)

		Screening	Treatment Period							Post-treatment Follow-up				
								Efficacy Assessment Independent of any dose delays						
Section	Day -35 to -1	W1D1 Visit	W2D1 Visit	W3D1 Visit	3-wkly Visits W4D1 W7D1 W10D1 etc.	Other Visits	24-Wk MDS Assessment Visit D169	Every 24 wks D337 D505 etc.	EOT Visit ^a	42-Day Follow-up	Long Term Follow-up	End of Study		
Section										6.2.2/11.1	6.3.1	6.3.2	11.2	
Time window				± 2 days	± 2 days	± 2 days	± 2 days	± 14 days ^b	± 14 days ^b		+2 days	± 7 days		
PK/ADA ASSESSMENTS (cont.)														
PK Sample Collection ^g Should be collected prior to IP dosing on a dosing day	6.5	—	X	X	X	W4D1 W10D1 W16D1 W22D1 for all subjects W13D1 W19D1 for dense PK subjects only	W1D3 W2D3 W17D1 W18D1 for dense PK subjects only	X		And every 12 weeks (± 14 days) from the 24-Week MDS Assessment Visit for up to 1 year from the first dose. Once a subject has been discontinued from treatment, PK samples may no longer be collected as long as ADA are not detectable.				—
ADA Sample Collection Should be collected prior to IP dosing on a dosing day	6.6	—	X	—	—	W4D1 W10D1 W16D1 W22D1 only	—	X	And every 12 weeks (± 14 days) from the 24-Week MDS Assessment Visit for up to 1 year from the first dose. If the subject was discontinued from study treatment earlier than 1 year from the first dose, additional samples will be collected if the last ADA is positive.				—	

Table 3: Table of Events (Continued)

		Screening	Treatment Period							Post-treatment Follow-up			
								Efficacy Assessment Independent of any dose delays					
Section	Day -35 to -1	W1D1 Visit	W2D1 Visit	W3D1 Visit	3-wkly Visits W4D1 W7D1 W10D1 etc.	Other Visits	24-Wk MDS Assessment Visit D169	Every 24 wks D337 D505 etc.	EOT Visit ^a	42-Day Follow-up	Long Term Follow-up	End of Study	
Section										6.2.2/11.1	6.3.1	6.3.2	11.2
Time window				±2 days	±2 days	±2 days	±2 days	±14days ^b	±14days ^b		+2 days	±7 days	

Table 3: Table of Events (Continued)

	Screening	Treatment Period								Post-treatment Follow-up			
							Efficacy Assessment Independent of any dose delays						
Section	Day -35 to -1	W1D1 Visit	W2D1 Visit	W3D1 Visit	3-wkly Visits W4D1 W7D1 W10D1 etc.	Other Visits	24-Wk MDS Assessment Visit D169	Every 24 wks D337 D505 etc.	EOT Visit ^a	42-Day Follow-up	Long Term Follow-up	End of Study	
Section										6.2.2/11.1	6.3.1	6.3.2	11.2
Time window			±2 days	±2 days	±2 days	±2 days	±14days^b	±14days^b		+2 days	±7 days		
FOLLOW UP													
Monitoring for progression to AML and other malignancies/pre-malignancies	6.1.20 6.3.2 10.5	After signing ICF and until 5 years from the first dose of IP, or 3 years from the last dose (whichever occurs later), or until death, lost to follow-up, withdrawal of consent for further data collection											
Posttreatment MDS therapies	6.3.2	–	–	–	–	–	–	–	–	–	X	X	X
Survival Follow-up	6.3.2	–	–	–	–	–	–	–	–	–	X	X	X

ADA = antidrug antibodies; AML = acute myeloid leukemia; BMA = bone marrow aspirate; BMB = bone marrow biopsy; D = day; ECG = electrocardiogram; ECOG = Eastern Cooperative Oncology Group; [REDACTED]; EOT = End of Treatment; EPO

= erythropoietin [REDACTED] – Anemia; Hep = hepatitis; HIV = human immunodeficiency virus; ICF = informed consent form; IP = investigational product; MDS = myelodysplastic syndromes; MOA = mechanism of action; PB = peripheral blood; PK = pharmacokinetics; RBC = red blood cell; RS = ring sideroblast; SARS-COV-2 = severe acute respiratory syndrome coronavirus 2; W = week; wkly = weekly.

^a End of Treatment (EOT) Visit procedures/assessments may not need to be repeated if previously performed within -7 days of EOT Visit. If a subject is discontinued during a regular scheduled visit, all EOT procedures should be completed at that visit. End of Treatment (EOT) Visit procedures/assessments may occur at 42-Day Follow-up assessment if subject is discontinued within ±7 days of 42-Day Follow-up assessment.

^b As central laboratory results from bone marrow and peripheral blood samples (ie, cytomorphology, cytogenetic analysis) are required as part of the MDS Disease Assessment, a 14-day window is allowed for the 24-Week MDS Disease Assessment Visit (ie, Day 169 ± 14 days) in order to account for sample collection and turnaround time of results. Please see Section 6.4.2 for details.

^c If screening assessments are performed within 2 days of W1D1, assessments of serum chemistry and hematology do not need to be repeated on W1D1.

^d In the event a local BM assessment for MDS diagnosis was made no more than 8 weeks before ICF signature, local BM samples/reports may be allowed for central “over read” after consultation with the sponsor and provided the central lab can confirm the diagnosis using the local samples/reports.

- ^e Collection of a BMB is only required when adequate aspirate is not attainable. To allow for cytomorphology assessment and cytogenetic analysis of the BMB please follow guidance for processing the sample provided in the study's Central Laboratory Manual.
- ^f Remaining BMA (after quantity sufficient is allocated towards cytomorphology and cytogenetics analysis) will be used for exploratory biomarker studies. An additional bone marrow procedure should not be performed for these samples. Refer to the central laboratory manual for additional information related to sample collection.
- ^g If a PK sample is drawn on a dosing day, the PK sample should be drawn prior to luspatercept dosing. All PK samples should be collected along the protocol defined "weekly" visits adapting to dose delays.
- ^h Questionnaires should be completed by the subject prior to IP administration.

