Serial measurements of safety and efficacy will occur at scheduled study visits as outlined in [Table 3](#). Laboratory analyses will be performed centrally. Local laboratories are allowed in cases when timely results are needed (eg, pre-dose Hgb assessments, study treatment dosing decisions, hematology assessments between clinic visits, adverse event). In these circumstances, a split sample should still be collected and sent to the central laboratory for analysis. Where discrepancies are present, results of the central laboratory will be used to determine response assessments.

An End of Treatment (EOT) evaluation will be performed for subjects who are withdrawn from treatment for any reason as soon as possible after the decision to permanently discontinue treatment has been made (Section 6.2.2).

Post-Treatment Follow-up Period

The Post-Treatment Follow-up Period consist of the 42-Day Safety Follow-up (Section 6.3.1), which includes (but is not limited to) the collection of adverse events (AEs), concomitant drugs and RBC-transfusion data, and the Long-term Follow-up (Section 6.3.2).

[figure not shown]
The transfusion data collection will continue until 8 weeks from the date of last dose of IP or from the date of the EOT Visit (whichever is later).

In addition, continuation of monitoring for other malignancies/pre-malignances and progression to AML will occur in the Long-term Post-Treatment Follow-up Period along with data collection of subsequent MDS therapies, and overall survival for 5 years from the date of the first dose of IP, or 3 years from the last dose (whichever occurs later) unless the subject withdraws consent

from the study, dies or is lost to follow-up. For that purpose, visits (which may consist of telephone contacts from the site) will be conducted every 12 weeks for the first 3 years from the date of last dose of IP and every 6 months thereafter, if applicable.

An antidrug antibodies (ADA) sample(s) may be required in the Post-Treatment Follow-up Period for subjects who terminate the Treatment Period with less than 1 year of ADA monitoring if a subject is ADA positive at the time of treatment discontinuation.

Figure 2: Overall Study Design

AE = adverse event; AML = acute myeloid leukemia; EOT = End of Treatment; IP = investigational product; MDS = myelodysplastic syndromes; Q3W = every 3 weeks; SC = subcutaneous.

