6.5. Pharmacokinetics

Blood samples will be collected to analyze luspatercept concentrations in serum in all subjects. At each PK time point, approximately 3 mL of peripheral blood will be collected and serum prepared as described in the in the study's Central Laboratory Manual. Blood samples for PK will be taken at the following visits during the study (also see [Table 3](#)):

- For the dense PK in the initial 10 subjects, W1D1 (must be collected before the first dose), W1D3, W2D1, W2D3, W3D1, W4D1, W10D1, W13D1, W16D1, W17D1, W18D1, W19D1, W22D1, 24-Week MDS Disease Assessment, and every 12 weeks from the 24-Week MDS Disease Assessment Visit for up to 1 year from the first dose.

- For the sparse PK in other 10 subjects, W1D1 (must be collected before the first dose), W2D1, W3D1, W4D1, W10D1, W16D1, W22D1, 24-Week MDS Disease Assessment Visit, and every 12 weeks (\pm 14 days) from the 24-Week MDS Disease Assessment Visit for up to 1 year from the first dose.

If a PK sample is drawn on a dosing day, the PK sample should be drawn prior to luspatercept dosing. All PK samples should be collected along the protocol defined “weekly” visits adapting to dose delays (see footnote g under [Table 3](#)). Once a subject has been discontinued from treatment, PK samples may no longer be collected as long as ADA are not detectable.

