6.6. Antidrug Antibody (ADA)

Blood samples will be collected to assess ADAs against luspatercept in serum. At each ADA sampling time point, approximately 3 mL of peripheral blood will be collected and serum prepared as described in the study’s Central Laboratory Manual. However, during the first year of treatment, an additional blood draw is not needed for the ADA test, as the ADA test will be conducted utilizing the PK samples obtained at the same visit. Blood samples for ADA will be taken at the following visits during the study (also see [Table 3](#)):

- W1D1 (must be collected before the first dose), W4D1, W10D1, W16D1, W22D1, 24-Week MDS Disease Assessment Visit and every 12 weeks (\pm 14 days) from the 24-Week MDS Disease Assessment Visit.

If an ADA sample is drawn on a dosing day, the ADA sample should be drawn prior to luspatercept dosing. If the last available ADA result at the end of treatment is positive, the subject may be asked to return to the clinical site for additional long-term follow up every 12 weeks (\pm 14 days) for up to one year after the first dose of luspatercept or until ADA are not detectable, whichever comes first.

The maximum ADA monitoring period will not exceed 1 year from the first luspatercept dose unless justified by safety reasons. ADA sampling per investigator’s or sponsor’s discretion is allowed and should be recorded as an unscheduled visit.

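### No ADA sample is scheduled at End of Treatment, and later ADA sampling depends on the last result being positive, so antibodies arising after the last scheduled draw may be missed in early stoppers

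*Combined protocol and SAP*

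**What the plan says.** Section 6.6 gives the ADA schedule as "W1D1 (must be collected before the first dose), W4D1, W10D1, W16D1, W22D1, 24-Week MDS Disease Assessment Visit and every 12 weeks". The EOT Visit is not on the list. In Table 3 the ADA row carries the same visits, followed by a merged cell with the 12-weekly rule up to 1 year. That cell is hard to read column by column, but the Section 6.6 list settles that EOT has no draw of its own.

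Sampling after treatment stops is conditional, and the condition is worded in three ways:

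- Table 3: "additional samples will be collected if the last ADA is positive".
- Section 6.6: "If the last available ADA result at the end of treatment is positive, the subject may be asked to return to the clinical site".
- Section 3.1, repeated in the Protocol Summary and Section 6.3.2: a sample may be required "if a subject is ADA positive at the time of treatment discontinuation".

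PK does not provide an assured back-up: "Once a subject has been discontinued from treatment, PK samples may no longer be collected as long as ADA are not detectable" (Section 6.5 and Table 3).

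Section 6.6 also permits extra ADA sampling at the choice of the investigator or the sponsor: this "discretion is allowed and should be recorded as an unscheduled visit". It limits the whole exercise: "The maximum ADA monitoring period will not exceed 1 year from the first luspatercept dose unless justified by safety reasons".

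ADA frequency, with its effects on efficacy, safety or PK, is a secondary endpoint over the first year (Table 2).

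**The concern.** Section 1.2.3.1 names faster drug clearance and hypersensitivity as the consequences of ADA. A subject who stops early because of a reaction or a lost effect is therefore among the most informative for this endpoint. Yet that subject's antibody status at stopping is not measured unless the stop happens to fall on a visit with an ADA draw. If the last scheduled draw was negative, the schedule asks for nothing more, however old that draw is.

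The wording in Sections 3.1 and 6.3.2 presupposes a status at discontinuation that the schedule does not obtain. Section 1.2.3 reports no earlier luspatercept exposure in Japanese subjects, and enrollment is about 20, so a single missed case is visible in the reported frequency.

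**Working it through.** The plan states no figure on this point, so the check is of the schedule itself.

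**Inputs.** ADA visits: Section 6.6 and Table 3. Dosing every 21 days: Section 3.1. The 24-week visit on Day 169, fixed regardless of dose delays: Section 6.4.2. Number of subjects, about 20: Section 4.1.

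**1. Scheduled ADA days.** The first day of week *k* is day 7(*k* − 1) + 1. W1, W4, W10, W16 and W22 give Days 1, 22, 64, 106 and 148. The 24-week visit is Day 169. Adding 84 days gives 253 and then 337; the next, 421, is beyond 1 year. The gaps are 21, 42, 42, 42, 21, 84 and 84 days.

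**2. Age of the last draw.** For a stop on day *d*, the age is *d* minus the latest scheduled ADA day not after *d*, before visit windows and dose delays.

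- Worst case before Day 169: 63 − 22 = 41 days (also 105 − 64 and 147 − 106).
- Worst case from Day 169 to 1 year: 252 − 169 = 83 days (also 336 − 253).
- Stop before W4D1: the only draw is Day 1, taken before the first dose. It cannot show an antibody induced by treatment.

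**3. Doses not covered.** Draws on dosing days are pre-dose. A subject who stops between W7D1 and W10D1 was last tested on Day 22, before the doses of Days 22 and 43. A subject dosed without delay who stops on Day 252 was last tested on Day 169 and has since had the doses of Days 169, 190, 211 and 232.

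**4. Dosing visits without a draw.** From W1 to W52 there are 18 nominal dosing visits. Ten carry no ADA draw:

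| Visit | Age of last ADA draw |
|---|---|
| W7, W13, W19, W28, W40, W52 | 21 days |
| W31, W43 | 42 days |
| W34, W46 | 63 days |

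If stop days were spread evenly (an assumption), the mean age would be 17.9 days for stops on Days 2–169 and 37.6 days for Days 170–365.

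**5. Dose delays.** Before Day 169 the dosing-visit draws move with the doses (note to Table 3), so a hold can lengthen the gap until the fixed Day 169 visit. After that the 12-weekly series runs from the fixed visit, and a hold does not lengthen it.

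**6. Effect on the frequency.** Each missed subject is worth 1/20 = 5 percentage points. As an illustration, one observed positive gives 1/20 = 5% (exact 95% CI 0.1%–24.9%); two would give 2/20 = 10% (1.2%–31.7%).

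**7. With a draw at EOT.** The age at the EOT Visit falls to 0 days, or at most 7 if the no-repeat window in Table 3 footnote a is used.

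**The case against.** The strongest reply is that the schedule already catches much of what matters. Antibodies present at the last scheduled draw are detected and trigger follow-up. A stop at a visit with an ADA draw is covered. The formal decisions on continued benefit in year 1 fall on Days 169 and 337, which are also nominal ADA days, and losing the hemoglobin response alone does not fail the benefit criterion while transfusion independence holds. Section 6.3.2 refers to Section 6.6, which defines its trigger as the last available result, so the mismatch in wording can be read away. A stop for hypersensitivity is an obvious occasion for a discretionary sample, and the sponsor as well as the investigator may ask for one.

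All of that stands, and it narrows the exposure to stops between draws. It does not remove it. Discretionary samples are taken when someone suspects antibodies, so they cannot replace a routine draw when the aim is a frequency.

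Three stronger readings are tempting but unsupported:

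- *Antibodies behind an early stop are never detected.* The routes just listed show otherwise.
- *Early stoppers are counted as ADA negative.* No rule in the documents classifies them. Section 9.7 says only that the frequency will be reported, and Section 9.2 leaves missing-data rules to the SAP.
- *The gap can reach 15 weeks after any dose hold.* Table 5 footnote c is attached to delays for suspected related adverse events of Grade 3 or higher, not to holds in general.

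**Conclusion.** The gap in the schedule is real and its length is certain: up to 41 days before Day 169 and up to 83 days after it, with no delays, or no post-dose draw at all for a stop before W4D1. That antibodies *may* be missed, and the frequency and its associations *may* be understated, follows from this. A reader might infer that the frequency *is* understated, or attach a total to it. The documents do not allow either, because they give no discontinuation rate, ADA incidence or time to onset. The only size they support is 5 percentage points per missed subject, taking 20 subjects as the denominator.

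The importance is modest. The endpoint is secondary and descriptive, and the HI-E test does not depend on it. The case for acting rests on the low cost of the change.

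**What to change.** 1. Add an ADA sample with paired PK at the EOT Visit in Table 3 and Sections 6.5 and 6.6, for any subject who stops within 1 year of first dose.
2. Make that EOT result the trigger for the 12-weekly ADA follow-up, so that Sections 3.1 and 6.3.2 refer to a status that is actually measured.
3. Reconcile *will* in Table 3 with *may* in the Protocol Summary and Sections 3.1, 6.3.2 and 6.6.
4. In the ADA summary, class as not evaluable at most those subjects with no post-baseline ADA sample. Do not extend this to everyone lacking a sample after the last dose. ADA monitoring stops at 1 year while treatment may continue, so that rule would drop long-term subjects with a complete negative series from the denominator and inflate the frequency.

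**Cost.** One tube of about 3 mL per subject stopping within the year, since Section 6.6 already runs the ADA test on the PK sample during the first year of treatment, plus assay cost for a few subjects. The EOT Visit already draws blood for hematology, chemistry, EPO, ferritin, biomarkers and the exploratory SARS-CoV-2 serology. Antibodies that first appear after a negative EOT sample would still go unseen; the change shortens the blind interval before stopping and does not cover the time after it.
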